8.1.4. Investigator's Global Assessment (IGA) of Atopic Dermatitis

The Investigator's Global Assessment of atopic dermatitis is scored on a 5-point scale (0-4), reflecting a global consideration of the erythema, induration and scaling. The clinical evaluator of atopic dermatitis will perform an assessment of the overall severity of atopic dermatitis and assign an IGA score and category as described in Table 5. The assessment will be a static evaluation without regard to the score at a previous visit.

Table 5. Investigator's Global Assessment (IGA) of Atopic Dermatitis Score

Score	Category	Description
0	Clear	Atopic dermatitis is cleared, except for any residual discoloration (post-inflammatory hyperpigmentation and/or hypopigmentation).
1	Almost Clear	Overall, the atopic dermatitis is not entirely cleared and remaining lesions are light pink (not including post inflammatory hyperpigmentation) and/or; have barely palpable hard thickened skin and/or papules and/or; have barely perceptible lichenification; excoriation and oozing/crusting are absent.
2	Mild	Overall, the atopic dermatitis consists of lesions that are light red; with slight, but definite hard thickened skin and/or papules; with slight, but definite linear or picked scratch marks or penetrating surface injury; with slight, but definite thickened skin, fine skin markings, and lichenoid scale; oozing/crusting is absent.
3	Moderate	Overall, the atopic dermatitis consists of lesions that are red; with easily palpable moderate hard thickened skin and/or papules; with moderate linear or picked scratch marks or penetrating surface injury; with moderate thickened skin, coarse skin markings, and coarse lichenoid scale; with slight oozing/crusting.
4	Severe	Overall, the atopic dermatitis consists of lesions that are deep, dark red; with severe hard thickened skin and/or papules; with severe linear or picked scratch marks or penetrating surface injury; with severe thickened skin with very coarse skin markings and lichenoid scale; with moderate to severe oozing/crusting.

8.1.5. Standardized Background Topical Therapy

Participants will be instructed to keep a daily record of use of standardized background topical therapy. At each visit, the participant's understanding of background topical therapy requirements (refer to Section 6.5.1) and adherence to the use of background topical therapy will be checked. Participants will be re-educated as required. Standardized background

topical therapy use and adherence with guidelines will be recorded daily in the participant eDiary during the treatment period, through the EOT visit:

- Non-medicated topical therapy must be applied at least twice daily to all body areas affected with AD starting on Day 1, and continued through the EOT visit;
- Refer to [Section 6.5.1](#) for required background medicated topical therapy during treatment through the EOT visit.

8.1.6. Patient-Reported Outcomes (PROs)

Participants will complete the PROs at the clinic prior to other clinical activities and study intervention administration. The PROs should be checked for completeness by the study site staff before proceeding with other steps of the clinical visit procedures. Compliance with scheduled PROs activities will be monitored. Delegated site staff will oversee the administration of PROs at site visits to ensure protocol compliance. Participants are given a handheld device to complete the PP-NRS on a daily basis. Delegated site staff will review compliance at each visit and counsel as appropriate. If a participant has repeated non-compliance, the participant should be re-trained on the device. If a participant is unable to complete the PROs on the handheld device due to documented difficulty using the technological devices or other limitation, the participant will be permitted to enter or remain in the study (for example, if the participant doesn't have internet access, he or she can complete the PROs offline and then they can upload the PROs to the internet when they return to the site and have internet access). In the event of electronic malfunction, a replacement device will be shipped to the site.

In instances where an electronic device is used to collect the PRO data, the electronic version may differ slightly in format or wording compared with the paper version to facilitate electronic implementation.

All PROs should be completed as per the [Schedule of Activities](#).

8.1.6.1. Peak Pruritus Numerical Rating Scale (PP-NRS)

The severity of itch (pruritus) due to AD will be assessed using the PP-NRS, a validated horizontal NRS.^{22,23} Participants will be asked to assess their worst itching due to AD over the past 24 hours on an NRS anchored by the terms “no itch” (0) and “worst itch imaginable” (10). This item will be administered to all participants. Participants will enter the PP-NRS assessment into an eDiary on a daily basis from the Screening visit through the Week 30 visit.

8.1.6.2. Dermatology Life Quality Index (DLQI)

The DLQI is a validated general dermatology questionnaire that consists of 10 items to assess participant-reported health-related quality of life (daily activities, personal relationships, symptoms and feelings, leisure, work and school, and treatment).²⁴ It has been extensively used in clinical trials for AD. The DLQI is a psychometrically valid and reliable instrument that has been translated into several languages, and the DLQI total scores have been shown to

be responsive to change. The minimally important difference for the DLQI has been estimated as a 3 to 5-point change from baseline.²⁵

8.1.6.3. EuroQol Quality of Life 5-Dimension 5-Level Scale (EQ-5D-5L)

The EQ-5D is a validated, standardized, generic instrument that is the most widely used preference-based health-related quality of life questionnaire in cost-effectiveness and health technologies assessment (HTA).²⁶⁻²⁹ Recently, a version was developed called EQ-5D-5L with 5 response levels on each dimension compared to the 3 response levels in the Euroqol Quality of Life 5-Dimension 3-Level Scale (EQ-5D-3L).²⁶⁻³²

Measurement properties of the EQ-5D-5L demonstrated to be a valid version of the 3-level questionnaire that improved measurements by adding discriminatory power, reducing the ceiling, and establishing convergent and known-groups validity.^{26,28,30,31} Both the EuroQol EQ-5D-3L and EQ-5D-5L versions are well-established instruments used to measure health states and utilities in various diseases areas and assess mobility, self-care, usual activities, pain/discomfort, anxiety/depression and health status using a VAS.^{29,33} The EQ-5D-3L was used previously in AD studies, including the dupilumab trials, to measure utilities.^{17,34-36}

8.1.6.4. Healthcare Resource Utilization (HCRU) Questionnaire

The HCRU is a 14-item questionnaire. This instrument is appropriate for use in participants aged 18 years and older.³⁷

8.1.6.5. Patient-Oriented Eczema Measure (POEM)

The POEM is a validated 7-item PRO measure used to assess the impact of AD recalled over the past week.³⁸⁻³⁹

8.1.6.6. Hospital Anxiety and Depression Scale (HADS)

The HADS is a validated 14-item PRO measure used to assess states of anxiety and depression over the past week.⁴⁰

8.1.6.7. Medical Outcomes Study (MOS) Sleep Scale

The Medical Outcomes Study Sleep Scale (MOS-Sleep) is a validated 12-item measure used to assess sleep quality in the pastweek. The instrument has been validated for use by participants 18 years and older.⁴¹

8.1.6.8. Skin Pain Numerical Rating Scale (SP-NRS)

The SP-NRS queries “worst skin pain” in the past 24 hours on an 11-point scale (0 [no skin pain] – 10 [worst skin pain imaginable]).⁴²

8.1.6.9. Asthma Control Questionnaire (ACQ)

Asthma control for all participants with a history of asthma, regardless of whether they are receiving medication for their asthma, should be assessed at times specified in the [Schedule of Activities \(SoA\)](#) using the Asthma Control Questionnaire (ACQ). The ACQ measures the adequacy of asthma control and change in asthma control which occurs either spontaneously

or as a result of treatment. The ACQ has 6 questions and participants are asked to recall how their asthma has been during the previous week and to respond to the symptom questions on a 7-point scale (0 = no impairment, 6 = maximum impairment). The questions are equally weighted and the ACQ score is the mean of the 6 questions and, therefore, between 0 (totally controlled) and 6 (severely uncontrolled).^{54, 55, 56}

8.1.7. Exploratory Accelerometry

AD is often accompanied by nighttime pruritus as well as disrupted and reduced overall sleep. Pruritus can lead to scratching, which can result in a worsening of the lesions and a further perpetuation of the disease. All of these contribute to altered quality of life for the participant. Quantitatively evaluating nighttime scratch and sleep via accelerometry using digital wearables and associated algorithms, to passively and continuously monitor participants in their “home environment,” provides an opportunity to examine new and distinct endpoints. Moreover, this evaluation contributes to the understanding how scratch and sleep endpoints correlate to currently used measures of AD severity.

Academic collaborative studies have shown nighttime scratch (number of scratch events and scratch duration) in AD participants correlated to the Investigator’s Static Global Assessment. In addition, accelerometry data processed by Pfizer algorithms to measure nighttime scratch and sleep quantity were able to distinguish between scratch and non-scratch movements, validated by thermal videography/annotation, and were able to detect sleep quantity, correlated to polysomnography measures (Clinicaltrials.gov study NCT03490877).⁵³ The amount and duration of nighttime scratching and the duration and arousals from the total sleep opportunity (nighttime sleep) will be assessed using accelerometry, in selected countries. Participants will wear wrist-worn, watch-like, accelerometry devices to continuously monitor the frequency of day and night time scratching and sleep disturbance for 1 week prior to the Day 1 visit, for 2 weeks following the Day 1 visit, and for 1-week periods during the weeks after the Week 12, Week 16, Week 20, and Week 26 visits.

Participation in accelerometry assessments is voluntary. Participants may refuse or remove the devices at any time, either entirely or for activities during which the devices are uncomfortable (ie, showering), without any impact on their study participation. Participants may also wear the devices over sleeves for comfort.

The following will be measured by accelerometry and subsequent algorithm assessment:

- Scratch (during the total sleep opportunity):
 - Number of scratching episodes;
 - Duration of scratching.
- Sleep (during the evening/major rest period):
 - Duration of the total sleep opportunity;

- Total sleep time (total time and percent time asleep);
- Sleep onset latency;
- Number of wake bouts (total and per hour of sleep);
- Wake after sleep onset (WASO);
- Sleep efficiency.

Data will remain blinded during the accelerometry endpoint processing in order to reduce bias when analyzing accelerometry data.

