Skin Pain NRS		X		X			X	X	X		X		Refer to Section 8.1.6.8
Asthma Control Questionnaire (ACQ)		X					X				X	X	Refer to Section 8.1.6.9 . Given to all participants with a prior diagnosis of asthma.

Procedure	Screening	Study Intervention Period										EOT / ED Visit	EOS Follow-up Visit (4 weeks after ED/EOT)	Notes
		1	2	3	4	5	6	7	8	9	10			
Visit		D1	D8	D15	D29	D57	D85	D113	D141	D169	D183	D211		
Study Day		WK0	WK1 Call	WK2	WK4	WK8	WK12	WK16	WK20	WK24 Call	WK26	WK30		
Study Week														
Visit Window (Days)	-28	0	±1	±1	±2	±3	±3	±3	±3	±3	±3	±3		
Optional Accelerometry														
Accelerometry training/retraining	X	X	X	X			X	X	X		X			Refer to Section 8.1.7
Issue/collect accelerometry devices	X	X		X			X	X	X		X			
Night Time Itch Accelerometry	X-----X	X-----X					X	X	X		X			
Hand Eczema Clinical Assessments														
History, subtype, clinical signs and extent	X													Refer to Section 8.1.8 .
Investigator's global assessment (IGA)	X	X		X	X	X	X	X	X		X	X		
Safety														
C-SSRS	X	X				X	X	X	X		X	X		Refer to Section 8.2.7.1
PHQ-8	X													Refer to Section 8.2.7.2
Serious and non-serious adverse event monitoring	X	X	X	X	X	X	X	X	X	X	X	X		Refer to Appendix 3 .
Contraception Check	X	X	X	X	X	X	X	X	X	X	X	X		Refer to Appendix 4 for contraceptive guidance.
Banked Biospecimens														
Banked Biospecimen for Genetics		X												Required to be collected for all participants (as local regulations and IRBs/ECs allow). Collect a 2 mL blood sample optimized for DNA isolation (Prep D1.5). Refer to Section 8.7.2 .

Procedure	Screening	Study Intervention Period									EOT / ED Visit	EOS Follow-up Visit (4 weeks after ED/EOT)	Notes
		1	2	3	4	5	6	7	8	9			
Visit		D1	D8	D15	D29	D57	D85	D113	D141	D169	D183	D211	
Study Day													
Study Week		WK0	WK1 Call	WK2	WK4	WK8	WK12	WK16	WK20	WK24 Call	WK26	WK30	
Visit Window (Days)	-28	0	±1	±1	±2	±3	±3	±3	±3	±3	±3	±3	
Banked Biospecimens for Biomarkers		X		X									Required to be collected for all participants (as local regulations and IRBs/ECs allow). Collect 4 mL blood sample optimized for biomarkers (Prep B2.5) and isolate serum. Collect a 2.5 mL blood sample optimized for RNA isolation (Prep R1). Refer to Section 8.8.4 .

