
 To compare the effect of abrocitinib 200 mg QD versus dupilumab on the frequency and duration of scratching during the night and sleep quantity in adult participants on background topical therapy with moderate to severe AD using wearable accelerometry devices. 	
 Number of scratching episodes during the evening sleep period that occur pre-treatment versus on-treatment, as derived from data analyses using wearable accelerometry monitors at scheduled time points; Duration of scratching episodes during the evening sleep period that occur pre-treatment versus on-treatment, as derived from data analyses using wearable accelerometry monitors at scheduled time points; Quantity of total sleep opportunity, total sleep time, percent time asleep, WASO, sleep onset latency, and number of wake bouts that occur pre-treatment versus on-treatment, as derived from data analyses using wearable accelerometry monitors at scheduled time points.

 To evaluate the efficacy of abrocitinib 200 mg QD in adult participants on background topical therapy with hand eczema. 	
 Response based on Investigator's Global Assessment (IGA) score of clear (0) or almost clear (1) (on a 5-point scale) and a reduction from baseline of ≥ 2 points at all scheduled time points.

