Participants may be re-screened once if they fail the screening evaluation for reasons related to incidental transitory conditions. Participants for whom screen failure is related to failing the disease severity (including extent of disease) inclusion criterion and who subsequently experience worsening AD, which in the investigator's judgement would make them eligible for participation, may be considered for re-screening. Such cases should be discussed with the Pfizer Medical Monitor (or designee) to determine if re-screening is appropriate.

Participants who continue to meet eligibility criteria at baseline will undergo Day 1 assessments and be randomized in a 1:1 ratio to receive abrocitinib 200 mg QD with dupilumab-matching placebo administered every other week or dupilumab 300 mg administered every other week (with a loading dose of 600 mg at baseline) with abrocitinib -matching placebo administered QD. Investigators, participants, and the sponsor study team will be blinded as to treatment group.

After Week 4, if medically necessary, participants with intolerable AD symptoms may receive locally-approved rescue therapy, at the investigator's discretion, pursuant to the following guidelines (refer to [Section 6.5.2](#)).

The total treatment period is 26 weeks. Participants discontinuing early from treatment, or who are otherwise ineligible for the B7451015 LTE study, will undergo a 4-week follow-up period. At Week 24 in the treatment period, all participants will cease injectable dupilumab or its matching placebo. Administration of abrocitinib 200 mg QD or its matching placebo will continue until Week 26. Efficacy and safety endpoints will be assessed throughout the entire study. Participants who complete the study through the Week 26 visit and are deemed eligible may enter the LTE Study B7451015.

See Section 10.12.3 for United Kingdom (UK) country-specific requirements.

For study estimands, refer to [Section 3.1](#).

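### The last accelerometry week falls after the Week 26 visit, so it cannot give the on-treatment value that the exploratory scratch and sleep endpoints call for

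*Protocol*

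**What the plan says.** The exploratory objectives in Protocol Section 3 compare the two drugs on night-time scratching and sleep. The first endpoint is "Number of scratching episodes during the evening sleep period that occur pre-treatment versus on-treatment", and scratch duration and sleep quantity use the same contrast at scheduled time points.

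Section 8.1.7 sets the wear periods: one week before Day 1, two weeks after it, and then "for 1-week periods during the weeks after the Week 12, Week 16, Week 20, and Week 26 visits". Participation is voluntary and limited to selected countries.

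Section 4.1 sets the treatment limits. "The total treatment period is 26 weeks". For the injection, "At Week 24 in the treatment period, all participants will cease injectable dupilumab or its matching placebo". For the tablet, "Administration of abrocitinib 200 mg QD or its matching placebo will continue until Week 26". Afterwards, "Participants who complete the study through the Week 26 visit and are deemed eligible may enter the LTE Study B7451015"; Section 6.1.1 sends everyone else into a 4-week post-treatment follow-up.

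The Schedule of Activities (SoA) marks Week 26 in its accelerometry rows, including "Issue/collect accelerometry devices". It shows no dispensing or observed dosing at Week 26 and no accelerometry mark at Week 30.

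**The concern.** At Weeks 12, 16 and 20, the week after the visit is an ordinary treatment week, so wearing the device then suits an on-treatment endpoint. Week 26 is different because the visit ends treatment. Carrying the same pattern forward puts the last recording in a period when some participants take no study drug and others may have entered another study. Neither group gives the on-treatment measurement the endpoint asks for, and nothing in the protocol labels that week as off-treatment or excludes it.

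At stake is the only accelerometry reading at month 6. Sections 4.2 and 8.1.7 also want scratch and sleep related to established severity measures. At Week 26 those measures are taken at the visit, while the device records the week that follows.

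**Working it through.** No sample size, power or alpha figure is involved. The check is study-day arithmetic.

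**Inputs.** Target days from the SoA: Week 12 = Day 85, Week 16 = Day 113, Week 20 = Day 141, Week 24 = Day 169, Week 26 = Day 183 (±3 days). Last injection at Week 24 and tablets until Week 26 (Section 4.1). A missed injection may be given up to 7 days late (Section 6.4.2).

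**Wear weeks.** A seven-night period starting on visit day V ends on V + 6.

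| Wear period | Nominal days | Scheduled dosing |
|---|---|---|
| After Day 1 (two weeks) | 1-14 | within |
| After Week 12 | 85-91 | within |
| After Week 16 | 113-119 | within |
| After Week 20 | 141-147 | within |
| After Week 26 | 183-189 | after the end |

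That makes 2 + 1 + 1 + 1 + 1 = 6 post-baseline wear weeks, of which one lies outside the treatment period.

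**Time since last dose in the final week.**
- Tablet, last taken on Day 182: 183 − 182 = 1 to 189 − 182 = 7 days. Last taken on Day 183: 0 to 6 days. Overall about 0-7 days, on a daily schedule.
- Injection on Day 169: 183 − 169 = 14 to 189 − 169 = 20 days, on a 14-day schedule.
- Injection given 7 days late, on Day 169 + 7 = 176: 183 − 176 = 7 to 189 − 176 = 13 days.

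The ±3-day visit window shifts the wear week but does not bring it before the visit.

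**The week before the visit, for comparison.** Days 176-182 lie within daily tablet dosing. They are 176 − 169 = 7 to 182 − 169 = 13 days after the scheduled last injection, so both arms are inside their dosing intervals.

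**Is there a safeguard in the analysis?** Protocol 9.4.1 leaves exploratory analyses to the SAP. The SAP version history records that exploratory endpoints were removed from Section 2. SAP 3.4 and 6.3 list no other endpoints, and Appendix 8 covers hand eczema, asthma control and resource use but not accelerometry. If the visit windows in SAP Appendix 2 were applied to device data, Days 183-189 would be labelled Week 26, since that window is Days 177-197.

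**The case against.** The strongest reply is that little depends on this. The current SAP has no accelerometry analysis; the endpoints survive only as exploratory protocol text for volunteers in some countries. No primary, key secondary or Type I error result is touched. That stands, and it limits the weight of the point.

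A reader might go further and infer that the month-6 comparison is biased by unequal washout of the two drugs. The documents do not support that. They give no half-life for either drug and do not describe what extension participants receive or when they start. They show different times since last dose and possible extension entry, and nothing about size or direction of bias. With a late Week 24 injection, the wear week can fall inside the two-weekly interval. If the last tablet is taken at the visit, the first night is within a day of a once-daily dose.

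A reader might also infer that the durability question in Section 4.2 is lost. It is not. That sentence concerns the study's efficacy as a whole, and month-6 itch and sleep are also measured at Week 26 by the daily itch score, SCORAD and the MOS Sleep Scale. Accelerometry after Weeks 12, 16 and 20 is unaffected.

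On device return, Appendix 13 arranges for used devices to be sent back, but only under public-emergency measures. It does not supply a routine return after Week 26.

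None of this removes the contradiction between the wear period and the endpoint wording.

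**Conclusion.** The point holds as an inconsistency between Section 8.1.7 and the exploratory endpoints. The Week 26 accelerometry period follows the scheduled end of treatment, so it cannot serve as an on-treatment value. It affects 1 of 6 post-baseline wear weeks, and that week is the only accelerometry recording at month 6. What it records is a mixture of residual effect, loss of effect and possible extension treatment, in proportions that depend on who enters the extension.

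This rests on nominal SoA days, on treatment ending as Section 4.1 states, and on the week after the visit meaning the seven nights from that visit. If the SoA instead intends final collection at Week 26, it contradicts 8.1.7, and the two must still be reconciled. If wear after Week 26 is intended, no return is scheduled at Week 30, and participants who roll over have no later visit in this study.

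The correction is worth making because it is cheap, but the consequence is minor.

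**What to change.** In Section 8.1.7 and the SoA, place the last wear week in the seven nights before the Week 26 visit. Use the existing Week 24 call for a reminder and the existing Week 26 visit for collection. State in 8.1.7 that this recording is the Week 26 on-treatment value.

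Assign it to Week 26 by its own rule rather than by SAP Appendix 2, because the first nominal night, Day 176, falls in the SAP's Week 24 window (Days 156-176).

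For data recorded under the current wording, label the week after Week 26 as off-treatment. Exclude it from the on-treatment endpoints and from the SAP Week 26 window (Days 177-197), and state how those devices are returned.

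The cost is one sentence in 8.1.7 and small SoA edits, with no added visit. The downside is that participants hold the device longer after Week 20. The documents give no battery life or storage capacity, so the sponsor must confirm that the device can manage two separate recordings between Weeks 20 and 26. If it cannot, labelling and excluding the post-Week 26 week, with a stated return route, is the fallback; it leaves no on-treatment accelerometry at month 6.
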